1.0 Project Summary/Abstract

[figure not shown]
Suicide is the second leading cause of death among female of reproductive age, and female suicide attempts occur most frequently around menses (perimenstrually), when estradiol (E2) and progesterone (P4) fall rapidly. A recent prospective study demonstrated that suicidal ideation (SI) and attempts peak perimenstrually in natural cycles, and that this perimenstrual worsening of SI can be prevented by administering stabilizing doses of E2+P4 (relative to placebo). Therefore, while E2+P4 withdrawal is a viable model of proximal suicide risk in females with SI, mechanisms are unclear. GABAergic neuroactive steroid metabolites of ovarian hormones (e.g., allopregnanolone), exert potent sedative and antidepressant effects; we hypothesize that acute perimenstrual withdrawal from these hormone metabolites may increase suicide risk by increasing hyperarousal and hopelessness. The **long-term objectives** of this research are to (1) use the menstrual cycle as a model to probe the proximal mechanisms of suicide, and (2) develop long-term treatments that eliminate hormonal contributions to suicide. The **objective of the current work** is to use a crossover placebo-controlled trial of E2+P4 stabilization (vs. natural E2+P4 withdrawal under placebo) in the perimenstrual weeks to probe behavioral (hopelessness, hyperarousal) and molecular/genetic (neuroactive steroid levels, mRNA expression for neurosteroidogenic enzymes) mediators of perimenstrual suicide risk. **Design:** In this mechanistic trial, 90 female outpatients with past-month SI will complete two counterbalanced conditions: (1) two weeks of placebo during natural perimenstrual E2+P4 withdrawal, and (2) two weeks of perimenstrual E2+P4 stabilization (.1mg/day transdermal estradiol + 200mg/day oral micronized progesterone) to prevent withdrawal. Five labs per condition will capture changes in GC-MS quantified neuroactive steroids and mRNA expression for neurosteroidogenic enzymes, and a wearable device (Oura Ring) will index basal body temperature and physiological arousal (heart rate, heart rate variability). Our app (*BiAffect*) will passively track arousal via movement and typing speed instability. 40 healthy controls (HC) with no SI will be recruited for a two-month long observational substudy, in which five lab visits across one menstrual cycle (timed identically to mirror the observations across one medication phase of the experimental trial) will capture baseline molecular/genetic changes for between-group comparisons. **Specific Aims.** Aim 1 is to evaluate hyperarousal and hopelessness as interacting mechanisms by which perimenstrual E2+P4 withdrawal (vs. experimental E2+P4 stabilization) increases proximal suicide risk. Aim 2 is to evaluate neuroactive steroid withdrawal as a mechanism by which perimenstrual E2+P4 withdrawal (vs. stabilization) increases proximal suicide risk. If appropriate, a multilevel path model will test a path in which E2+P4 withdrawal (vs. stabilization) causes neuroactive steroid withdrawal, which increases in hopelessness and hyperarousal, which in turn increases proximal suicide risk. Aim 3 (substudy) is to characterize GABA-A receptor gene expression plasticity across the cycle in individuals with and without perimenstrual changes in affect and suicide risk. **Relevance.** By conducting a mechanistic experiment to probe the mediators of a known cause of proximal suicide risk, the proposed research responds to public calls from the NIMH-sponsored Suicide Research Prioritization Agenda to identify modifiable causes of *proximal* suicide risk.

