We define **hyperarousal** (RDoC Arousal and Regulatory Systems) as (1) self-reported agitation and overwhelm, (2) psychomotor agitation (smartphone accelerometer instability/movement^{13,14}), (3) behavioral reactivity to external stimuli (smartphone typing speed instability^{13,14}, attentional bias toward angry/fearful faces on task¹⁵), and (4) physiological hyperarousal (reduced resting parasympathetic autonomic function¹⁶, increased sympathetic and decreased parasympathetic autonomic function during an emotionally arousing task).

[figure not shown]
We define **hopelessness** as a state of despair *arising due to repeated experiences of loss or sustained threat* (RDoC Negative Valence Systems). It will be measured primarily as self-reported hopelessness using the Beck Hopelessness Scale (BHS)¹⁷, and we will measure lifetime and daily exposure to loss and threat^{18,19}.

We define **proximal suicide risk** as the presence and severity of self-injurious thoughts and behaviors as assessed dimensionally using the Adult SI Questionnaire (ASIQ)²⁰ and categorically using the Self-Injurious Thoughts and Behaviors Interview -Revised (SITBI-R). These instruments assess for passive and active SI; suicide plans; aborted, interrupted, and actual suicide attempts; and suicide death. Although non-suicidal self-injury (NSSI) is a distinct but related phenomenon, we also consider NSSI as an index of proximal risk given its predictive validity for suicide attempt²¹.

[figure not shown]
Premise for Aim 1a

Perimenstrual Hormone Withdrawal Causes Proximal Suicide Risk

In the first prospective study¹² of daily suicide risk in females with SI (K99MH109667), the PI found that proximal suicide risk peaks perimenstrually, during periods of natural hormone (E2+P4) withdrawal (Fig. 3). 38 females with past-month SI completed daily ratings on the ASIQ²⁰ across a baseline menstrual cycle. ASIQ scores peaked during the perimenstrual weeks relative to late follicular week, $\gamma=-.88$, $p<.001$ and early luteal week, $\gamma=-.56$, $p<.001$. We also observed greater odds of endorsing suicidal planning items on perimenstrual vs. non-perimenstrual days (OR=4.29, $p<.001$). 28 of 30 participants reported the highest mean SI perimenstrually. *These data support the premise that suicide risk peaks perimenstrually.*

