3.0 Objectives/Aims

Our aim is to test the **central hypothesis** is that perimenstrual E2+P4 withdrawal induces rapid withdrawal from calming GABAergic neuroactive steroids, which in turn increases hyperarousal and hopelessness, which then interact to cause proximal suicide risk (Figure 1). P4 is metabolized to GABAergic neuroactive steroids, and E2 promotes expression of enzymes that convert P4 to neuroactive steroids⁹³. Perimenstrual E2+P4 withdrawal may increase suicide risk by causing rapid withdrawal from the antidepressant⁹ and sedative^{11,10} effects of neuroactive steroids⁹⁴, as well as withdrawal from the antidepressant effects of E2⁹⁵. Our preliminary experimental work strongly suggests that perimenstrual E2+P4 withdrawal (and neuroactive steroid withdrawal) heightens proximal suicide risk via hopelessness⁶⁵ and hyperarousal^{12,66}.

Figure 1. Peri-menstrual Hormone Withdrawal and Proximal Suicide Risk

Design: Using the PI’s hormone withdrawal paradigm (K99MH109667¹²), a new sample of 90 completers female outpatients with past-month SI will complete two counterbalanced conditions: (1) natural perimenstrual E2+P4 withdrawal (placebo), and (2) perimenstrual E2+P4 stabilization. Five labs per condition will capture changes in neuroactive steroids, mRNA expression for neurosteroidogenic enzymes, physiological arousal, behavioral indices of arousal, and interview/self-report indices of proximal suicide risk, hopelessness, and hyperarousal. Our app (BiAffect) will passively track indices of arousal including psychomotor agitation (accelerometer) and reactivity (typing speed variability). Additionally, Metricwire will passively track movement using smartphone sensors. 40 healthy controls (HC) will complete five labs across one observational cycle to characterize 1) normative cycle-related variation in neuroactive steroids and mRNA expression, and 2) group-related differences (i.e., past-month SI vs HC) in trajectories of GABAAR subunit change across the cycle.

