AIM 1: To evaluate hyperarousal and hopelessness as interacting mechanisms by which perimenstrual E2+P4 withdrawal (vs. experimental stabilization) increases proximal suicide risk. We predict that **(1a)** individuals will demonstrate greater proximal suicide risk during perimenstrual E2+P4 withdrawal (placebo) than during perimenstrual E2+P4 stabilization, an effect mediated by **(1b)** indices of hyperarousal, **(1c)** indices of hopelessness, and **(1d)** their interaction (i.e., with hopelessness predicting suicide risk only during hyperarousal).

AIM 2: To evaluate neuroactive steroid withdrawal as a mechanism by which perimenstrual E2+P4 withdrawal (vs. stabilization) increases proximal suicide risk. We expect that E2+P4 withdrawal (vs. stabilization) will induce neuroactive steroid withdrawal to some degree in all participants. However, we predict that the effect of hormone withdrawal (vs. stabilization) on proximal suicide risk at each lab will be mediated by **(2a)** degree of reduction in serum neuroactive steroid levels and **(2b)** degree of reduction in mRNA expression for neurosteroidogenic enzymes. We will also evaluate

within-person links between neuroactive steroids and all behavioral constructs; if appropriate, a multilevel mediation model will test the full model in Fig. 1.

AIM 3: To characterize GABA_{AR} gene expression plasticity across the cycle in individuals with and without perimenstrual changes in affective and suicide risk. In the HC group, we hypothesize that gene expression for $\alpha 4$ and δ subunits (GABRA4 and GABRD genes, respectively) are upregulated and $\gamma 2$ (GABRG gene) is downregulated in the midluteal (high ALLO) and perimenstrual (ALLO decline) phases compared to the midfollicular phase (low ALLO). We also hypothesize that clinical group moderates the effect of cycle phase on GABA_{AR} composition, such that the group with perimenstrual increases in affective symptoms and suicide risk shows higher slope of midluteal-to-perimenstrual change in $\alpha 4$ and δ subunits, and lower $\gamma 2$ subunit replacement of δ subunit expression than the HC group.

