Behavioral Reactivity to External Stimuli: Typing speed instability will be calculated as a momentary and daily measure of reactivity to phone-based stimuli. Instability metrics will be calculated as the root mean square successive difference (rMSSD). This metric evaluates variability in consecutively recorded typing speeds and encapsulates both the size and the temporal order of within-subject fluctuations. In a prior study, our team has demonstrated that daily typing instability is able to prospectively predict disturbed mood¹²².

A variety of other relevant indices will be available from the BiAffect Keyboard, including but not limited to the number of errors made while typing, diurnal activity patterns and inferred hours of sleep, and amount of phone usage¹²³.

Physiological Arousal: Oura Ring Devices will collect data on the subject's body temperature, heart rate, interbeat interval) of sufficient quality for heart rate (HR) and heart rate variability (HRV) analysis.

Metricwire is a multi-platform (iOS and Android) smartphone app (www.metricwire.com) that has been previously used in many health and behavioral studies. Participants who have a compatible mobile device will be emailed a link and given a lab-generated email and password to sign up for the study. The app is used for a variety of methods in the literature; here, it will be used as an adjunct application to capture accelerometer and movement data from the smartphone's sensors. This is being collected in addition to the movement data from BiAffect since the sampling rate is higher and it can collect data even when the participant is not typing. Metricwire data will be collected up until July 31st, 2023. After this date, participants will no longer be enrolled into the Metricwire app and no data will be collected.

Smartphone-based assessments for HC participants (Aim 3 substudy).

HC participants will complete the following as described above: daily symptoms survey, BiAffect app (psychomotor changes, behavioral reactivity to external stimuli), Metricwire. HC participants will **not** receive Oura rings for physiological arousal.

Participant Compensation.

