Testing for group differences between participants with past-month SI and HC. We hypothesize that clinical group moderates the effect of cycle phase on GABA_{AR} composition, such that the primary experimental group shows higher slope of midluteal-to-perimenstrual change in $\alpha 4$ and δ subunits, and lower $\gamma 2$ subunit replacement of δ subunit expression than the HC group. In one model of N=80 total participants, we will test the interaction of group and cycle phase on gene expression outcomes. We also hypothesize a correlation with symptoms, such that increases in $\alpha 4$ and δ subunit expression will be associated with increases in individuals with perimenstrual increases in SI. We also predict that even in the HC group, higher-than-average $\alpha 4$ or δ subunit expression will be associated with higher-than-average negative affect (e.g., depressed mood, anxiety, irritability, or perceived stress). We predict that higher $\gamma 2$ expression will be associated with lower negative affect and perceived stress. We will calculate a person-mean for each subunit's expression (mean level across 5 visits) and a deviation score at each visit (visit level minus person mean). We will test overall correlations (e.g., do participants with higher mean $\alpha 4$ expression have higher negative affect?) and interaction with cycle phase (e.g., does a perimenstrual increase in $\alpha 4$ expression *compared to person-mean* correlate with an increase in negative affect?). To further refine hypotheses, we will generate credible intervals using Bayesian methods in the context of multilevel modeling.

POWER ANALYSIS

80 completers achieves 80% power to detect conventionally small-to-medium sized effects that, in our estimation, are clinically meaningful (i.e., $f^2 = .10$, which would mean that the interaction of condition and phase had uniquely accounted for 10% of the variance in the outcome in the perimenstrual window; Selya et al., 2012, “*A Practical Guide to Calculating Cohen’s f^2 , a Measure of Local Effect Size*”). We posit that if hormone withdrawal (vs. experimental stabilization) does not account for at least 10% of the variance in the outcome during this critical risky window of the menstrual cycle, then this line of research, which involves significant participant burden, is not worth pursuing further.

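### Aim 3 is worded around perimenstrual change, but its moderation test compares past-month SI with healthy controls, so that test alone cannot attribute a difference in cycle slope to perimenstrual change

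*Protocol*

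**What the plan says.** The Project Summary (protocol 1.0) frames Aim 3 as a study of "gene expression plasticity across the cycle in individuals with and without perimenstrual changes in affect and suicide risk". Section 3.0 words the moderation hypothesis in the same spirit, "such that the group with perimenstrual increases in affective symptoms and suicide risk shows higher slope of midluteal-to-perimenstrual change in" the α4 and δ subunits. Section 10.0 repeats the hypothesis with a different subject, "such that the primary experimental group shows higher slope of midluteal-to-perimenstrual change in" those subunits, and gives the test: in one model of 80 participants, "we will test the interaction of group and cycle phase on gene expression outcomes". The design paragraph of section 3.0 agrees with section 10.0; it announces "group-related differences (i.e., past-month SI vs HC) in trajectories of GABAAR subunit change across the cycle".

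Entry to the SI group depends on ideation in the past month (section 4.1, criterion 11). Entry to the HC group depends on never having had ideation and having no DSM-5 diagnosis within five years. The only criterion that uses cyclical ratings is criterion 14, which removes treatment-seekers with confirmed PMDD. Under criterion 3, SI participants must be in mental health care or willing to start it, and controls must not be in care for a psychiatric condition.

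Section 10.0 also plans person-mean and deviation scores for subunit expression. These are to be related to negative affect, overall and by phase, with a prediction for controls too, and a further hypothesis links rising expression to perimenstrual increases in SI. The SAP (2019) covers Aims 1 and 2 only.

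**The concern.** The aim asks about a property of the person's cycle: does she worsen perimenstrually or not? The moderator in the test is recruitment status. Between section 3.0 and section 10.0 the SI group takes the place of the group with perimenstrual increases, and nothing in eligibility or analysis ties the two together.

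At stake is what a positive group-by-phase result would mean. Women in the SI group differ from controls in ideation history, recent diagnosis and care. Any of these could alter how subunit expression moves from the midluteal to the perimenstrual phase. Under the section 3.0 wording, such a difference would be credited to perimenstrual change. Section 2.0 wants subunit expression as a possible biomarker of cyclical affective change, and group membership does not measure that change.

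**Working it through.** **1. The plan's own figure.** Section 10.0 gives N = 80 for the group-by-phase model, without a derivation. Stated completers are 90 SI and 40 HC, and 90 + 40 = 130. The figure 80 fits 40 + 40, but no rule for choosing 40 SI participants is given. No effect size, alpha or power is stated for Aim 3, so there is nothing further to reproduce.

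**2. What the contrast estimates.** Let p and r be the shares of the SI and HC groups with perimenstrual change. Let D be the difference in midluteal-to-perimenstrual expression slope between women with and without that change. Let C be any slope difference between the groups at equal change status, due to diagnosis, care or anything else. Then

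group contrast = (p − r) × D + C.

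If D = 0, the contrast equals C, so it can be non-zero with no link to perimenstrual change. This point needs no figures.

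**3. Size of the dilution when C = 0.**
- p: section 2.0 reports that "28 of 30 participants reported the highest mean SI perimenstrually", so p = 28/30 = 0.933 (exact 95% CI 0.78 to 0.99).
- r: not in the documents; assumed 0 to 0.30.
- Alpha: two-sided .05, assumed.
- D: set so that perfect classification gives 80% power, so the standardised effect is 1.960 + 0.842 = 2.802.

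Power = Φ(2.802 × (p − r) − 1.960). Sample-size ratio = 1/(p − r)².

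| r | p − r | N ratio | Power |
|---|---|---|---|
| 0 | 0.93 | 1.15 | 74% |
| 0.10 (assumed) | 0.83 | 1.44 | 65% |
| 0.20 (assumed) | 0.73 | 1.86 | 54% |
| 0.30 (assumed) | 0.63 | 2.49 | 43% |

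First row: 2.802 × 0.933 − 1.960 = 0.655, and Φ(0.655) = 0.74. The results are the same for 40 v 40 and 40 v 90, because D is rescaled to 80% power in each.

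**4. Direction of the net bias.** At r = 0.10 the shortfall is 1 − 0.83 = 0.17 of D. A C of 0.17 × D in the same direction would cancel the dilution, and a larger C would inflate the contrast. The documents give no value for C.

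**5. Are the data there?** Section 6.0 says "HC participants will complete the following as described above: daily symptoms survey", and the SI group completes the same survey every evening. A change score can therefore be formed in both groups.

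**The case against.** The strongest reply is that section 10.0 does not ignore perimenstrual change. Its deviation scores ask whether a woman's perimenstrual rise in expression goes with a rise in her negative affect, and it links rising expression to perimenstrual SI increases. That stands. A reader might infer that Aim 3 as a whole cannot be answered; the documents do not support this, and the limit applies to the group-by-phase test alone. However, the symptom analyses are loosely specified, and they neither enter perimenstrual change as the moderator nor separate it from group.

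Three further points also stand.
- A reader might infer that any lasting difference between the groups would pass as receptor plasticity. It would not: a constant level difference falls in the group main effect, and only a difference in slope matters.
- A reader might set 28 against the 38 women with baseline-cycle ratings and conclude that the dilution is severe. Section 2.0 reports 28 of 30 and does not say that the other eight lacked a perimenstrual peak.
- Controls have no lifetime ideation, and no HC exception is stated for criterion 14. If the aim means change in affect and suicide risk jointly, r may be near zero. Only change in affect alone makes a larger r plausible.

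It is also fair that the section 10.0 subheading already calls this a comparison of past-month SI with HC, and that section 2.0 calls the substudy exploratory. The wording to correct is therefore in sections 1.0 and 3.0.

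**Conclusion.** The mismatch between aim and moderation test is in the text and needs no calculation. Group by phase compares past-month SI with HC. By itself it cannot show that a difference in slope belongs to perimenstrual change, because diagnosis and care differ between the groups by design.

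The statistical cost is less certain. On the pilot figure alone the dilution is modest: a factor of 0.93, and power of about 74% in place of 80%. Factors of 0.83 to 0.63 rest on an assumed 10% to 30% of controls with perimenstrual affect change. The pilot figure is itself a weak marker, since it records where mean SI was highest, not how far it rose, and it says nothing about affect. A reader might infer that the contrast is necessarily biased toward zero; the documents do not establish this, because confounding could push it the other way.

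This is worth correcting before analysis. It is a limit on interpretation in an exploratory substudy, not a fault that disables it.

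**What to change.** 1. Keep the planned group-by-phase model. In sections 1.0 and 3.0, state its hypothesis and conclusion as past-month SI versus HC.
2. Pre-specify a second model in section 10.0. For each woman, compute a continuous perimenstrual change score from daily-survey negative affect: the mean of days +11 to +17 minus the mean of the luteal days before the day +7 dosing visit. Use the placebo cycle for SI and the observational cycle for HC. Test change score by phase on subunit expression, with group by phase in the same model.
3. Repeat the change-score model within the SI group alone, where recruitment status cannot explain the result.
4. Let conclusions about perimenstrual change rest on change score by phase.
5. State which condition's SI visits enter the Aim 3 models, and reconcile N = 80 with 90 and 40 completers.

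The cost is protocol wording and one extra interaction in a small substudy, with no new data collection. A score from a single cycle carries measurement error, which will attenuate its own interaction. If SI status tracks perimenstrual change as closely as 28 of 30 suggests, the score may also be collinear with group.

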
2.0 Background/Scientific Rationale

Among females of reproductive age, suicide is the second leading cause of death, accounting for 13% of all female deaths in America¹. Although males are more likely to die by suicide (due to higher-lethality methods), females are three times as likely to experience suicidal ideation (SI) or attempt suicide². This sex difference manifests between puberty³ and menopause⁴, implicating fluctuations in ovarian hormones. Despite this, *no published longitudinal or experimental studies have directly examined ovarian hormone effects on suicide risk*.

In cross-sectional studies, suicide attempts occur most frequently peri-menstrually—that is, in the weeks before and during menses—when the ovarian hormones E2 P4 fall rapidly. The perimenstrual weeks have been repeatedly linked with greater risk of suicidal behaviors in cross-sectional hospital and postmortem studies^{5–8}. While this further implicates hormone changes in proximal suicide risk, *the impact of this work is limited by a lack of longitudinal or experimental data, and a lack of data regarding mechanisms*.

One possible mechanism of perimenstrual suicide risk is rapid perimenstrual withdrawal from E2 and P4 (Fig 2), as well as withdrawal from the antidepressant⁹ and sedative^{10,11} effects of their **GABAergic neuroactive steroid metabolites**. The PI's recent longitudinal and experimental studies (K99-MH109667¹²), which form the premise for the proposed work, provide the first (1) longitudinal evidence that daily SI and behavior peak perimenstrually, and (2) experimental evidence that E2+P4 withdrawal causes increased perimenstrual suicide risk that can be prevented by administering stabilizing doses of E2+P4¹². **The proposed mechanistic trial** responds to the RFA by integrating the PI's experimental paradigm with molecular, genetic, and behavioral measurements to examine the mechanisms by which perimenstrual E2+P4 withdrawal (vs. experimental stabilization) increases proximal suicide risk. We examine mediation across levels of analysis, including changes in neuroactive steroid metabolites (serum neuroactive steroid levels, neuroactive steroid biosynthetic enzyme mRNA expression in peripheral monocytes) as well as hopelessness and hyperarousal.

Defining and Operationalizing Behavioral Constructs

We define **hyperarousal** (RDoC Arousal and Regulatory Systems) as (1) self-reported agitation and overwhelm, (2) psychomotor agitation (smartphone accelerometer instability/movement^{13,14}), (3) behavioral reactivity to external stimuli (smartphone typing speed instability^{13,14}, attentional bias toward angry/fearful faces on task¹⁵), and (4) physiological hyperarousal (reduced resting parasympathetic autonomic function¹⁶, increased sympathetic and decreased parasympathetic autonomic function during an emotionally arousing task).

[figure not shown]
We define **hopelessness** as a state of despair *arising due to repeated experiences of loss or sustained threat* (RDoC Negative Valence Systems). It will be measured primarily as self-reported hopelessness using the Beck Hopelessness Scale (BHS)¹⁷, and we will measure lifetime and daily exposure to loss and threat^{18,19}.

We define **proximal suicide risk** as the presence and severity of self-injurious thoughts and behaviors as assessed dimensionally using the Adult SI Questionnaire (ASIQ)²⁰ and categorically using the Self-Injurious Thoughts and Behaviors Interview -Revised (SITBI-R). These instruments assess for passive and active SI; suicide plans; aborted, interrupted, and actual suicide attempts; and suicide death. Although non-suicidal self-injury (NSSI) is a distinct but related phenomenon, we also consider NSSI as an index of proximal risk given its predictive validity for suicide attempt²¹.

[figure not shown]
Premise for Aim 1a

Perimenstrual Hormone Withdrawal Causes Proximal Suicide Risk

In the first prospective study¹² of daily suicide risk in females with SI (K99MH109667), the PI found that proximal suicide risk peaks perimenstrually, during periods of natural hormone (E2+P4) withdrawal (Fig. 3). 38 females with past-month SI completed daily ratings on the ASIQ²⁰ across a baseline menstrual cycle. ASIQ scores peaked during the perimenstrual weeks relative to late follicular week, $\gamma=-.88$, $p<.001$ and early luteal week, $\gamma=-.56$, $p<.001$. We also observed greater odds of endorsing suicidal planning items on perimenstrual vs. non-perimenstrual days (OR=4.29, $p<.001$). 28 of 30 participants reported the highest mean SI perimenstrually. *These data support the premise that suicide risk peaks perimenstrually.*

Stabilization of E2+P4 Prevents Perimenstrual Worsening of Suicide Risk. In the PI's recently-completed double-blind crossover trial¹² (K99MH109667) in 30 females with past-month SI, SI severity once again peaked during perimenstrual weeks in the placebo condition (black solid line, Fig 4), and perimenstrual administration of E2 (.1mg/day) and P4 (200mg/day) in the stabilization condition prevented this increase in SI (dashed red line; Cond \times Phase $\gamma=-.75$, $p<.0001$). Further, as predicted, perimenstrual risk was then shifted in the active condition, appearing only later during withdrawal from exogenous hormones ($\gamma=.59$, $p<.0001$). This further demonstrates the causal effect of E2+P4 withdrawal on proximal suicide risk. When results were person-standardized, the impact of stabilization was roughly a 1 person-standard-deviation condition difference in severity of SI change. Further, more participants reported suicidal behaviors during placebo vs. active (NSSI: 18 vs. 10; preparatory acts: 5 vs. 1; aborted attempts: 2 vs. 0). This experiment supports the premise that E2+P4 withdrawal causes proximal suicide risk.

In order to develop safe long-term treatments that eliminate hormonal contributions to suicide, we need information about the mechanisms by which E2+P4 withdrawal cause proximal suicide risk. Unfortunately, recent meta-analytic work demonstrates that poor progress has been made toward predicting attempts among ideators²¹, and little is known about reliable time-varying prediction of proximal suicide risk²². Therefore, candidate mediators in the present proposal are informed primarily by our general understanding of the most robust mechanisms E2+P4 withdrawal, and preliminary findings from our prior trial of E2+P4 stabilization in females with past-month SI. Below, we argue that neuroactive steroid withdrawal, hopelessness, and hyperarousal are strong candidate mediators of E2+P4 withdrawal effects on proximal suicide risk.

Premise for Aim 1b

Hopelessness as a Mediator of E2+P4 Withdrawal Effects on Suicide Risk

Hopelessness features prominently in suicide theories. Although hopelessness has recently been framed as primarily a predictor of SI rather than suicide attempt or death, large prospective studies demonstrate the predictive validity of baseline hopelessness for suicide death in inpatients ($n=102$)²³ and outpatients ($n=1,958$)²⁴, and a meta-analysis of longitudinal studies reports a role for baseline hopelessness as a *prospective* predictor of attempt (OR=1.95), and death (OR=2.15)²⁵. Although hopelessness is one of the best-studied constructs in suicide research, little evidence is available about dynamic changes in hopelessness and proximal suicide risk. One recent report described the use of daily surveys to evaluate links between risk factors and SI. They found that fluctuations in hopelessness successfully predicted SI severity *at the next time point* across two samples, suggesting that surges in hopelessness increase proximal suicide risk²⁶.

E2+P4 Withdrawal Causes Hopelessness. E2+P4 withdrawal paradigms increase behavioral despair in animals. While despair can be triggered by withdrawal from E2²⁷ or P4²⁸, combined E2+P4 withdrawal is most similar to the perimenstrual phase. Among other likely mechanisms of E2+P4 withdrawal on hopelessness (e.g., serotonergic), we focus on E2+P4 as regulators of GABAergic neuroactive steroids, since prevention of neuroactive steroid formation using finasteride administration (i.e., abrupt neuroactive steroid withdrawal) recapitulates E2+P4-withdrawal-induced despair in animals, even when E2 or P4 remain high²⁹. In susceptible females, withdrawal from E2+P4 provokes sadness^{27,30,31}; however, a key

limitation of this literature is that few experimental or longitudinal studies specifically examine the impact of hormone withdrawal on hopelessness.

Preliminary Data: Perimenstrual E2+P4 withdrawal (vs. stabilization) increases daily hopelessness. In our recent trial (K99MH109667), we found that ovarian steroid withdrawal (under placebo) was associated with *increased* daily reports of hopelessness in females with past-month SI, and that this was prevented by administering stabilizing doses of E2+P4 (Condition X Phase $\gamma = -.73$, $p = .023$). Further, controlling for daily within-person changes in hopelessness partially mediated the effect of E2+P4 stabilization on SI severity (95% CI for Indirect Effect: -.21 to -.53). *This preliminary work supports the premise that E2+P4 withdrawal causes perimenstrual hopelessness, effects which may explain proximal perimenstrual risk for suicide.*

Premise for Aim 1c

Hyperarousal as a Mediator of E2+P4 Withdrawal Effects on Suicide Risk

Hyperarousal, defined as physiological hyperarousal, psychomotor agitation, and agitation or overwhelm³², is an acute precipitant of suicidal behavior³²⁻³⁵. In a meta-analysis, disturbances in arousal were among the strongest predictors of suicidal behavior²⁵; however, this is an understudied area. In a meta-analysis focused specifically on *agitation*, agitation predicted suicide attempts³⁵. However, little within-person work has been done to understand the time course of risk. Similarly, altered cardiovascular reactivity is linked to SI and attempts³⁶⁻³⁸, but no work examines acute changes in physiological arousal and proximal suicide risk.

E2 and P4 withdrawal causes hyperarousal. In animals, E2+P4 withdrawal increases indices of hyperarousal, including autonomic function³⁹ and heightened behavioral reactivity to stimuli¹⁰. Withdrawal from neuroactive steroids, which occurs to varying degrees during E2+P4 withdrawal in the perimenstrual phase, causes reactivity-promoting alterations in associated brain circuitry, including the amygdala⁴⁰⁻⁴², the bed nucleus of the stria terminalis^{42,43}, and the periaqueductal grey^{44,45}. Further, variables linked to suicidal ideation and behavior, including social stress⁴⁶ and isolation⁴⁷, lifetime abuse⁴⁸, impulsivity⁴⁹, Borderline Personality Disorder^{50,51}, and PTSD^{52,53}, intensify effects of E2+P4 withdrawal on GABAergic neuroactive steroids or hyperarousal.

Preliminary Data: Perimenstrual E2+P4 withdrawal (vs. stabilization) increases daily hyperarousal. In the previous hormone stabilization trial¹², we found increased daily agitation⁵⁴ and overwhelm⁵⁵ during perimenstrual E2+P4 withdrawal under placebo, which was prevented by administering stabilizing doses of E2+P4 (Cond \times Phase $\gamma = -.87$, $p < .0001$; Cond \times Phase $\gamma = -.92$, $p < .0001$). Controlling for within-person levels of self-reported agitation on the Brief Agitation Measure partially mediated the effect of E2+P4 stabilization on SI severity (95% CI for Indirect Effect: -.30 to -.55) and probability of endorsing suicide planning²⁰ (95% CI for Indirect Effect: -.18 to -.34). *This work supports the premise that E2+P4 withdrawal causes hyperarousal in the form of self-reported agitation, which may explain proximal perimenstrual risk for suicide.*

Preliminary Data: Our recent meta-analysis demonstrates that the perimenstrual phase is robustly associated with the lowest parasympathetic nervous system activity, consistent with physiological hyperarousal during perimenstrual E2+P4 withdrawal. Our meta-analysis (under review) aimed to quantify within-person variations in measures of cardiac vagal activity (indices such as heart rate variability, that capture parasympathetic innervation of the heart) across different cycle phases. A literature search following the PRISMA-Statement yielded 38 empirical studies (N=1,018) reporting repeated measures of cardiac vagal activity in at least two cycle phases. We found a significant decrease in parasympathetic activity from the late follicular (stable P4 and neuroactive steroids) to the premenstrual phase ($d = -1.32$, 95% CI [-2.35, -0.29]) during E2+P4 withdrawal. *This meta-analysis supports the premise that autonomic hyperarousal is heightened during perimenstrual E2+P4 withdrawal. The proposed trial would experimentally test if physiological hyperarousal is caused by E2+P4 withdrawal, and whether these changes mediate effects on suicide risk.*

[figure not shown]
Hopelessness and agitation are core features of depression and hyperarousal, respectively. Notably, several studies document that the intersection of depression and hyperarousal signals increased risk of suicide attempt in inpatients and outpatients³³. Although this has primarily been discussed in the context of “mixed” states related to bipolar disorder, the intersection of depression and hyperarousal is not unique to bipolar disorder, and may increase proximal suicide risk³⁵. Thus, for the purposes of the proposed work we hypothesize that hopelessness translates into proximal suicide risk only during hyperaroused states such as psychomotor agitation, physiological hyperarousal, and subjective agitation or overwhelm.

Because they rapidly change neuronal excitability, neuroactive steroids are excellent candidate mediators of proximal suicide risk. The neuroactive steroids allopregnanolone (**ALLO**; 3 α ,5 α -THP) and pregnanolone (**PA**; 3 α ,5 β -THP) are cholesterol-derived molecules (see Fig. 5 for biosynthetic pathway) that act as potent positive allosteric modulators at synaptic and extrasynaptic GABA_A receptors, amplifying Cl⁻ ion flux during GABA binding at GABA_A receptors⁵⁶. Administration of ALLO induces rapid sedative, antidepressant, anxiolytic, anesthetic, analgesic, and anticonvulsant effects⁵⁷. Therefore, ALLO withdrawal can cause mood disturbances (i.e., hopelessness) as well as psychomotor agitation and autonomic hyperarousal³⁹. The biosynthetic pathways for these neuroactive steroids are illustrated in Figure 5. ALLO is produced via a two-step process in which P4 is first converted into **5 α -DHP** by the enzyme **5 α -reductase type 1 (5 α -RI)**, which is converted to ALLO by the enzyme **3 α -hydroxysteroid dehydrogenase type 2 (3 α -HSDII)**. PA is produced via a similar process substituting 5 β -reductase. Our review will focus on ALLO, since it is the best studied.

Neuroactive steroid withdrawal mediates many deleterious behavioral effects of E2+P4 withdrawal. Many deleterious behavioral effects of E2+P4 withdrawal are mediated by ALLO withdrawal, as evidenced by the fact that blockade of P4 metabolism to neuroactive steroids (i.e., acute ALLO withdrawal) recapitulates the depressogenic and anxiogenic effects of E2+P4 withdrawal even when E2+P4 remain stable⁹. Further, direct experimental manipulation of ALLO withdrawal also causes these behavioral phenotypes⁵⁸.

